### 3.4 Primary study endpoint

- Find a direct and significant correlation between increased IAP level (iatrogenic induced and controlled), ICP, ONSD, vasopressin release and urine output
- Two different pathophysiological mechanisms could potentially elicit an increase in ICP (pneumoperitoneum and PEEP), so that the most accounting mechanism may be investigated and in what proportion

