## **2. OBJECTIVES**

In a standard operative setting as for sleeve gastrectomy, endotracheal ventilation is routinely administered to patients under general anesthesia. Positive expiratory end-pressure (PEEP) effect on increasing IAP is controversial, still its effect on increasing intracranial pressure (ICP) is widely accepted.

The aim of this study is to investigate any direct correlation between increased intrathoracic pressure, intraabdominal pressure and intracranial pressure, following a controlled elevation in intraabdominal pressure and intrathoracic pressure (PEEP). The second end-point is to investigate any correlation between elevated intracranial pressure and vasopressin release, urine output and urine and serum osmolality by measuring their values at different time-points.

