#### **3.3 Study Interventions and Measures:**

Patients selected and consented for elective surgery will undergo standard of care and additional measurements during and after surgery. These measurements involve minimal risk as the probability and magnitude of physical or psychological harm anticipated in the research are not greater in and of themselves than those ordinarily encountered in daily life, or in routine medical, dental, or psychological examinations. In order to support our pathophysiological hypothesis, we identified 4 different conditions in which the measurements should be done:

- A) Baseline
- B) Patient under general anesthesia, 10-15 minutes after insufflation of pneumoperitoneum at 15mmHg, PEEP at 5cmH2O or lowest setting
- C) 10-15 minutes after stabilization of PEEP at 10cmH2O, pneumoperitoneum still at 15 mmHg
- D) 10-15 minutes after desufflation of pneumoperitoneum and basal mechanical ventilation

Measurements include:

4

V 4 , 2018 01/16/2019 NCT Number: NCT03707054

---

-Intraabdominal pressure IAP: assessed via laparoscopic insufflator, set at 15 mmHg as a standard value for all laparoscopic procedures

-Intrathoracic pressure: indirectly measured by variability of peak expiratory pressures

-Urine collection: Urine output will be measured every shift by the nursing staff from the beginning of surgery to post-operative day 1. The use of Foley catheters during these laparoscopic procedures is dependent on the surgeon's judgment based on patient's co-morbidities. However, in order to participate in this study a Foley catheter needs to be inserted, so the patient will receive a Foley catheter. It will be removed Post-operative day 1.

-Urine osmolality prior to surgery and 8-12 hours post-surgery

-Serum/plasma collection: blood draws to evaluate specific values of

-Plasma Vasopressin (ADH)

-Serum osmolality

-Mean arterial pressure: noninvasive standard anesthesia monitoring

-Pulmonary expiratory end-pressure (PEEP): anesthesiologists routinely adapt PEEP in order to maintain an optimal ventilation, especially in obese patients and during laparoscopy

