## **5. STATISTICAL PLAN**

This is the sample size calculation for identifying significant increase in vasopressin release after an elevation in intra-abdominal pressure.

Study Design:

Patients undergoing a Sleeve Gastrectomy are to be enrolled to participate in the study. 4 different conditions in which the measurements should be done during and after the surgery:

A) Baseline

- B) 10-15 minutes after insufflation
- C) 10-15 minutes after stabilization
- D) 10-15 minutes after desufflation

Primary aim:

Expecting 20-25% increase in the normal value of vasopressin significant for the study purpose.

Assumptions:

- The normal range value of vasopressin is from 1 to 4pg/ml. According to the number stated in the reference articles, we assume the coefficient of variation is 0.455.
- The type I error rate for the overall test comparing the three groups will be 0.05.
- There would be six pairwise group comparisons: A vs B, A vs C, A vs D, B vs C, B vs D, C vs D; the type I error rate for each comparison will be 0.0083(Bonferroni correction) and the data were assumed to be log-normal distributed.
- Power was computed based on 80%.

Statistical Method:

Repeated measures ANOVA is used to compare the means score of vasopressin across four different conditions. The comparison between any two conditions is accessed using paired t-test. To adjust for the multiple test problem, Bonferroni correction is applied and the type I error rate for each comparison will be 0.0083.

Result:

Plausible sample size for any two conditions comparison with 25% vasopressin increase should be 57

9

V 4 , 2018 01/16/2019 NCT Number: NCT03707054

---

Table 1. Sample Size Calculation			
Increase Rate	Nominal Power	Actual Power	N
20%	0.8	0.802	83
20%	0.9	0.900	104
25%	0.8	0.806	57
25%	0.9	0.902	71
30%	0.8	0.803	42
30%	0.9	0.907	53

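### Sections 2, 3.4 and 5 name three different primary questions, and the planned vasopressin analysis tests only the IAP-vasopressin part of the stated primary endpoint

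*Combined protocol and SAP*

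**What the plan says.** Three sections of the combined protocol and SAP state what the study is chiefly for.

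- **Section 2 (Objectives).** The aim is to "investigate any direct correlation between increased intrathoracic pressure, intraabdominal pressure and intracranial pressure". Vasopressin comes next: "The second end-point is to investigate any correlation between elevated intracranial pressure and vasopressin release, urine output and urine and serum osmolality".
- **Section 3.4 (Primary study endpoint).** The first bullet is "Find a direct and significant correlation between increased IAP level (iatrogenic induced and controlled), ICP, ONSD, vasopressin release and urine output". The second asks which of pneumoperitoneum and PEEP accounts for a rise in ICP, "so that the most accounting mechanism may be investigated and in what proportion".
- **Section 5 (Statistical Plan).** The primary aim is a 20-25% rise in vasopressin. The methods are "Repeated measures ANOVA is used to compare the means score of vasopressin across four different conditions", then six paired t-tests at 0.0083 each. N is 57 for a 25% rise at 80% power.

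Section 3.3 fixes what can be analysed. IAP is "assessed via laparoscopic insufflator, set at 15 mmHg as a standard value for all laparoscopic procedures". ONSD is measured by ultrasound, and Section 1.1 presents that technique as the tool for assessing ICP. Urine output is recorded once per nursing shift up to postoperative day 1. Urine osmolality is taken before surgery and 8-12 hours after it.

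**The concern.** A primary endpoint should be one quantity with one prespecified analysis. Here vasopressin is second in Section 2, one of five variables in Section 3.4, and the sole primary in Section 5. Most of what Section 3.4 declares has no analysis in Section 5.

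Two things are at stake. Three candidate primaries leave room to choose after the data are seen. And whoever has to report the Section 3.4 correlation must invent the method. A simple choice, correlating all ONSD and vasopressin readings, could pass off a shared response to inflation as a direct link between the two.

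**Working it through.** **1. Endpoint against analysis**

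| Component of Section 3.4 | What Section 3.3 provides | Analysis in Section 5 |
|---|---|---|
| IAP with vasopressin | 15 mmHg for everyone at B and C; no value or method given for A and D | Yes: ANOVA and paired t-tests |
| ICP | Not in the list of measurements; ONSD is the surrogate | None |
| ONSD | Ultrasound | None |
| ONSD with vasopressin | Both collected | None |
| Urine output | Per shift, not per condition | None |
| Pneumoperitoneum versus PEEP | B and C differ in PEEP at the same IAP | C vs B for vasopressin only; nothing for ONSD and no apportionment |

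IAP has no spread between patients and no graded levels during insufflation, so correlation with IAP reduces to a contrast between conditions. ICP and ONSD stand as two variables in the endpoint, but one is collected, so no correlation between them can be estimated. The expected results in Section 3.4 predict changes in urine output and urine osmolality at B and C, which the Section 3.3 schedule cannot show.

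**2. The plan's own N**

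Inputs from Section 5: CV 0.455, ratio 1.25, alpha 0.0083, power 0.80, log-normal data. Assumed, because the plan does not state them: a two-sided test and a raw-scale within-patient correlation of 0.4.

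- SD of log vasopressin = √ln(1 + 0.455²) = √0.1882 = 0.434.
- Log-scale correlation = ln(1 + 0.4 × 0.2070)/0.1882 = 0.0796/0.1882 = 0.423.
- SD of the log difference = 0.434 × √(2 × (1 − 0.423)) = 0.466.
- Standardised effect = ln(1.25)/0.466 = 0.2231/0.466 = 0.479.
- Paired t-test (noncentral t): N = 57, power 0.806, as stated. The same inputs reproduce all six rows of Table 1.

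With raw-scale correlations of 0, 0.3, 0.5 and 0.7, N would be 96, 66, 48 and 30. A single B-versus-A test at two-sided 0.05, with correlation 0.4, would need 37. So 57 belongs to a mean change in vasopressin for any of six comparisons at 0.0083.

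**3. What 57 patients can detect as a correlation (80% power, two-sided)**

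Fisher's z gives r = tanh[(z for alpha + z for power)/√(n − 3)]. The sum of z values is 2.80 at 0.05 and 3.48 at 0.0083.

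- A-to-B changes, one pair per patient: tanh(2.80/√54) = 0.36; tanh(3.48/√54) = 0.44.
- Within-patient model adjusted for condition: 56 × 3 = 168 residual degrees of freedom, so √166 replaces √54. This gives 0.21 and 0.26.

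For a true r of 0.3 between changes, power is 0.62 at 0.05 and 0.36 at 0.0083.

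**4. Illustration of an unguarded correlation**

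Simulated: N=57, four conditions, no direct ONSD-vasopressin link, both variables raised at B and C. The vasopressin shift is 0.2231/0.434 = 0.51 SD, from the plan's own effect. The ICC (taken as equal for both variables) and the ONSD shift are assumptions; the documents give neither. Share of trials significant at 0.05:

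| ICC | ONSD shift (SD) | Pooled | Within-patient, unadjusted |
|---|---|---|---|
| 0.42 | 0.2 | about 12% | about 11% |
| 0.2 | 0.51 | about 16% | about 25% |
| 0.42 | 0.51 | about 21% | about 40% |
| 0.7 | 0.51 | about 28% | about 86% |

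In the mildest corner (ICC 0.2, shift 0.2 SD) both rates are about 8%. The condition-adjusted slope and the correlation of A-to-B changes stay near 5% throughout.

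**The case against.** The strongest defence is that correlation is loose wording for a change between conditions. IAP is not constant: each patient goes from no pneumoperitoneum (A) to 15 mmHg (B, C) and back (D). The expected results in Section 3.4 are written in those terms, and Section 5 sizes the study for a vasopressin rise after IAP is raised. This stands for the IAP-vasopressin component, which the planned tests address validly.

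The defence also notes that ONSD is the declared surrogate for ICP. That stands too; what remains is that the endpoint lists both as separate variables. Nor can one say that IAP goes unrecorded at A and D. The limitations text mentions a baseline measure, ambiguously; the documents simply give no value or method there.

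Finally, Section 5 contains no pooled correlation, so the simulated error rates are not a property of the plan. That is right, and they serve only to guide the choice of method. Adjusting for condition is likewise a choice. It removes the IAP-driven change common to both variables, which is part of the authors' hypothesis, so the estimand must be stated.

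None of this supplies an analysis for ONSD, urine output, the ONSD-vasopressin link or the apportionment, or reconciles the three primaries.

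**Conclusion.** The concern holds as a mismatch between endpoint and analysis. Three sections name three primary questions, and Section 5 tests one component of the Section 3.4 endpoint. That part of the finding rests on the text alone.

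A reader might infer that the primary endpoint cannot be tested at all, or that the trial will answer nothing. The documents do not support that: the on/off change in IAP is real within each patient, and the vasopressin contrasts test it. A reader might also take 40% as the trial's false-positive rate. It is one cell of an illustration of an analysis the plan does not contain, and it moves from about 8% to 86% with the assumed ICC and ONSD shift.

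The detectable correlations (0.36 and 0.21 at 0.05; 0.44 and 0.26 at 0.0083) assume complete data on 57 patients. The model figures also assume the same within-patient association in every condition.

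**What to change.** 1. Name one primary endpoint in Sections 2, 3.4 and 5. The sample size supports log vasopressin across A-D with paired contrasts at 0.0083. If B versus A alone is made primary, state its alpha. State also the within-patient correlation and sidedness behind 57.
2. Replace correlation with IAP by the A-D contrasts for vasopressin and, as a secondary endpoint, for ONSD. Use B−A for pneumoperitoneum (together with anesthesia, if A precedes induction, so define A) and C−B for added PEEP. Because C always follows B, say that C−B also carries elapsed time.
3. Replace ICP in the endpoint by ONSD as a surrogate for ICP, and limit conclusions to ONSD.
4. Take urine output out of the condition-level primary endpoint and report it descriptively over the recorded shifts. Drop the prediction of urine osmolality at B and C, or mark it as not observable on this schedule.
5. Test the ONSD-vasopressin link as secondary: a mixed model of log vasopressin on within-patient-centred ONSD, with a fixed condition effect and a random patient effect, supported by the correlation of A-to-B changes. Say that it estimates association beyond the shared condition shift, and give the detectable r at the alpha chosen.

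Cost: wording in three sections and some extra analysis, with no added patients or measurements. The price is that urine output leaves the primary endpoint; keeping it there would require collection timed to A-D.

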#### **Expected results:**

- At higher IAPs (time-points B and C), an increase in vasopressin serum levels, a decrease in urine output and renal function with increased urine osmolality are expected. A significant increase in ONSD is also expected.
- At IAP normalization (time-points A and D), a decrease in vasopressin serum levels and restoration of renal function and urine osmolality are expected.

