### 3.5 Primary safety endpoints

- The study should be stopped if the patients experience any symptoms or complications due to the interventions implemented.
- The need of opioid will be assessed by the pain score scale and will be restricted to the minimum level required to control the patient's pain and to

provide optimal comfort, as opioid administration may be a confounding element in vasopressin release

- All the measurements will pose minimal risk to the patient. ONSD assessment is non-invasive and safe. Urine collection is routinely assessed during Sleeve Gastrectomy by means of a Foley catheter. Blood draws pose only minimal risk to the patient. Urine output is measured every shift per the nursing staff as standard of care.
- Variations in PEEP level are currently performed during general anesthesia, especially in obese patients and during laparoscopy; according to this study design are supposed to be transient and controlled, therefore not potentially dangerous to patient's intra- and post-operative ventilation

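### The urine collection schedule gives no output value for any of conditions A–D and no osmolality sample at B, C or D, so urine output cannot be tested against IAP level or condition

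*Combined protocol and SAP*

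**What the plan says.** Section 3.4 puts urine output in the primary endpoint, as one of the quantities to be correlated with the controlled IAP level. The Expected results under that section predict, for B and C, "an increase in vasopressin serum levels, a decrease in urine output and renal function with increased urine osmolality are expected". For A and D they predict that renal function and urine osmolality are restored.

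Section 3.3 opens with the general statement that "we identified 4 different conditions in which the measurements should be done". B and C fall during pneumoperitoneum, and D is "10-15 minutes after desufflation of pneumoperitoneum and basal mechanical ventilation". The same section then gives urine a schedule of its own:

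- Output: "Urine output will be measured every shift by the nursing staff from the beginning of surgery to post-operative day 1". Section 3.5 repeats this: "Urine output is measured every shift per the nursing staff as standard of care".
- Osmolality: "Urine osmolality prior to surgery and 8-12 hours post-surgery".

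The Limitations text sets urine collection apart from the measurements made during and around surgery. Section 3.3 sets IAP at 15 mmHg for all patients. Section 5 plans an analysis of vasopressin only and names no method for urine.

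**The concern.** The predictions are tied to time-points that last minutes, but the collection is tied to nursing shifts and to two samples on either side of the operation. If the protocol is followed exactly, the database will hold nothing that shows whether urine output fell or osmolality rose at B or C, or whether osmolality had recovered by D.

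Urine output is named in the primary endpoint, and intraoperative urine that is not read at the time cannot be recovered later. Patients also bear a burden for these data. Section 3.3 says that a Foley catheter is otherwise at the surgeon's discretion but is required for participation, and Section 4.2 excludes patients who refuse one.

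**Working it through.** **1. The plan's own figure.** The only calculated figure is the vasopressin sample size in Section 5 (CV 0.455, log-normal data, alpha 0.0083 per comparison, 80% power, 25% increase, N = 57). Two inputs are assumed because they are not stated: a two-sided test and a within-patient correlation of 0.4.

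- Log variance: ln(1 + 0.455²) = 0.188.
- Variance of the paired log difference: 2 × [0.188 − ln(1 + 0.4 × 0.455²)] = 2 × (0.188 − 0.080) = 0.217, so SD = 0.466.
- Standardised effect: ln(1.25)/0.466 = 0.223/0.466 = 0.479.
- The noncentral t then gives N = 57 with power 0.806, as in Table 1. The other five rows also reproduce.

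No urine quantity enters this calculation, so nothing below changes it.

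**2. Claims against schedule.**

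| Quantity | Expected (under 3.4) | Collected (3.3, 3.5) | Values specific to A / B / C / D |
|---|---|---|---|
| Urine output | Lower at B and C | Shift totals from the start of surgery | none / none / none / none |
| Urine osmolality | Higher at B and C; restored at A and D | Before surgery; 8–12 h after | pre-surgery sample / none / none / none |
| Renal function | Lower at B and C; restored at A and D | No measure listed | none / none / none / none |

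Output therefore has 0 of 4 condition-specific values, and osmolality has 0 of 3 samples at B, C and D. Output collection begins with surgery, so there is no earlier output to serve as a baseline. For renal function, Section 7.2 mentions basic laboratory results but does not say which.

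**3. Why analysis cannot repair this.** A correlation with IAP needs IAP to vary. By design every patient has 15 mmHg at B and C, so the planned variation lies between insufflated and non-insufflated conditions in the same patient. A shift total runs across those conditions and gives one number for all of them. Across patients the set pressure is a constant, and a correlation with a constant is undefined.

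**4. Dilution in a shift total (illustration).** The documents give neither shift length nor duration of pneumoperitoneum; 8–12 h and 60–90 min are assumed. With otherwise constant urine flow:

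- Share of a full shift = minutes of pneumoperitoneum / (60 × shift hours).
- Lowest: 60/720 = 8.3%. Highest: 90/480 = 18.8%.
- Change in the shift total = fractional fall in flow × share. A 50% fall gives 0.5 × 8.3% = 4.2% to 0.5 × 18.8% = 9.4%.
- If the first record covers only the last 4 h of a shift (assumed), the share rises to 60/240 = 25% up to 90/240 = 37.5%.

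**The case against.** The strongest reply is that the longer urine window looks deliberate. Sections 3.3 and 3.5 agree on it, and the Limitations text acknowledges it. The link to B, C and D appears only under Expected results, which is neither an endpoint nor an analysis. On this view it is the wording of the expectations that is out of place, and rewording them would remove most of the conflict. That stands, and the fix below offers it as an alternative. It does not settle the endpoint, which names IAP level as well as urine output.

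A reader might also infer more than the documents support:

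- *That the urine component cannot be analysed at all.* Shift totals, and the change in osmolality from before to after surgery, can still be correlated between patients with vasopressin or optic nerve sheath diameter. That is a weaker question, but an answerable one.
- *That Section 2 contradicts the schedule.* It asks for "urine output and urine and serum osmolality by measuring their values at different time-points". Samples before surgery and 8–12 h after it are different time-points, so there is no contradiction.
- *That urine output is predicted to recover at D.* The text names renal function and urine osmolality there, not output.
- *That a shift total carries no trace of pneumoperitoneum.* The shares in the illustration rest on assumed durations and are larger if the first record covers only part of a shift.

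**Conclusion.** The point holds in this form: under the stated schedule the urine changes expected at B and C, and the osmolality recovery expected at D, cannot be observed, and the urine-output part of the primary endpoint cannot be tested against IAP level or condition. This follows from the schedule alone and needs no assumption. Renal function is predicted to change without a listed measure.

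The figure of about 8–19% of a full shift is only an illustration, resting on assumed shift and pneumoperitoneum lengths and constant background flow. Section 5 takes vasopressin as its primary aim and plans no urine test, so the powered comparison and N = 57 are untouched. The mismatch should be fixed, but it does not undermine the vasopressin comparison.

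**What to change.** **Preferred.** Use the catheter already required.

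- Record the time of insertion, then timed cumulative urine volumes at six moments: the start of a defined pre-insufflation interval, insufflation, B, C, desufflation and D. Report mL/h for each of the five intervals.
- Keep the first reading and the desufflation reading. Without the first there is no baseline rate. Without the second, the interval from C to D mixes the remaining pneumoperitoneum with recovery.
- Record IV fluid per interval and use it as a covariate.
- Where assays allow, take a catheter urine sample for osmolality with each blood draw.
- Add to Section 5 a sentence naming the urine analysis.

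**Cost.** Six readings per patient and, if the pre-surgery sample serves for A, up to three more osmolality assays, plus amendment wording. Volumes will be small: at an assumed 30–100 mL/h, 10–15 minutes yields 30 × 10/60 = 5 mL to 100 × 15/60 = 25 mL, so measurement error will be appreciable.

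**If this is refused.** Reword the Section 3.4 endpoint and the Expected results so that the urine outcomes are perioperative (shift totals; osmolality before surgery against 8–12 h after), name their analysis, and make no urine claim about IAP level or about B, C and D.

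**Either way.** Delete renal function or name the measure used.
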